6.3. Missing Data

Efficacy Endpoints

Any methods for dealing with missing data where manipulation of the data is planned for each efficacy endpoint are covered in the relevant section of efficacy analysis below.

Adverse Event Dates, Relationship and Severity

Missing day will be imputed as the first day of month for all start dates, and as the last day of the month for all stop dates.

Missing month will be imputed as January for all start dates and as December for all stop dates.

The imputed start date will be compared to the informed consent form date (ICF) to ensure it makes sense and falls on or after the ICF date. If it falls before the ICF, then set the imputed start date to the ICF.

If the stop date is complete, and the imputed start date is after the actual stop date, then the start date will be imputed as the stop date.

The imputed stop date will be compared to the last study date or death date and will be set to the last study date or death if the proposed imputed date is beyond the later of these dates.

Completely missing start dates for AEs will be imputed as the start date of treatment, if the end date is completely missing. Completely missing start dates for AEs will not be imputed, if the end date is completely available, as the position of the end date as either before or after the first dose date will be used to determine treatment-emergent adverse event (TEAE) status. No imputations will be done for subjects who did not receive study drug.

TEAEs will be considered treatment-related if relationship information is missing. Similarly, TEAEs will be considered severe if the severity information is missing.

Concomitant Medication Dates

Missing day will be imputed as the first day of month for all start dates, and as the last day of the month for all stop dates.

Missing month will be imputed as January for all start dates and as December for all stop dates.

The imputed start date will be compared to the ICF to ensure it makes sense and fall on or after the ICF date. If it falls before the ICF date, then set the imputed start date to the ICF.

If the stop date is complete, and the imputed start date is after the actual stop date, then the start date will be imputed as the stop date.

The imputed stop date will be compared to the last study date or death date and will be set to the last study date or death if the proposed date is beyond the later of these dates.

Completely missing start dates for concomitant medications will be imputed as the start date of treatment, if the end date is completely missing. Completely missing start dates for concomitant medications will not be imputed, if the end date is completely available, as the position of the end date as either before or after the first dose date will be used to determine the status of

whether a medication is prior or concomitant. No imputations will be done for subjects who did not receive study drug.

Medical/Allergy History Dates

For partial start date in medical history and allergy history eCRF pages, impute as follows:

- Missing day is set to 1 if the same year and month as the informed consent date. Otherwise set it to 15
- Missing month is set to Jan if the same year as the informed consent date. Otherwise set it to July
- Missing month and day are set to Jan 1 if the same year as the informed consent date. Otherwise set it to July 1.

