7.9.1. Adverse Events

All AEs will be coded and classified according to MedDRA version 23.0 or later. All nonallergic AEs will be graded according to the NCI CTCAE Version 5.0. All allergic AEs will be graded according to the Consortium of Food Allergy Research (CoFAR) grading scale, with Grade 1 (mild symptoms), Grade 2 (moderate symptoms), Grade 3 (severe symptoms), Grade 4 (life-threatening symptoms) and Grade 5 (death). The relationship of AE to study drug will be judged by the investigator as related or not related.

Treatment-emergent AEs (TEAE) are defined as any event that starts or worsens in severity on or after the first dose of study drug until 30 days after the last dose of study drug. TEAEs will be considered treatment-related if relationship information is missing. Similarly, TEAEs will be considered severe if the severity information is missing. Imputed values for relationship, severity or onset date will be used for incidence summaries, while the actual values will be used in data listings. The AEs not considered to be a TEAE will be included in subject listings, but not summarized.

The AESIs include the following categories: anaphylaxis, any AE leading to the use of epinephrine (e.g., EAI), and Eosinophilic Esophagitis (EoE).

All reported AEs will be classified into SOC and PT. Summaries will be ordered by descending incidence of SOC and PT within each SOC for the overall column. Summaries displayed by PT only will be ordered by descending incidence of PT for the overall column. In addition, exposure adjusted incidence rates of TEAEs, treatment-emergent serious adverse events (TESAEs) and treatment-emergent AESIs will be presented, where exposure incidence rate is defined as the total number of events divided by the total number of subject-years at risk during the study treatment period, or defined as the total number of events divided by the total number of study drug doses received during the study treatment period.

An overview summary of the number and percentage of subjects with at least one of the following AE categories will be presented by treatment group and overall.

- Any TEAE
- Any TESAE
- Any TEAE related to study drug

- Any TEAE due to accidental exposure
- Any TEAE due to food challenge
- Any TEAE due to other study procedure
- Any TESAE related to study drug
- Any TESAE due to accidental exposure
- Any TESAE due to food challenge
- Any TESAE due to other study procedure
- Any TEAE resulting in drug discontinuation

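### The SAP's rule for partial adverse-event start dates moves events that began just after first dose to before it, so they leave the TEAE tables

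*SAP*

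**What the plan says.** SAP section 6.3 has separate rules for partial and wholly missing adverse-event start dates.

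- **Partial dates.** "Missing day will be imputed as the first day of month for all start dates" and "Missing month will be imputed as January for all start dates". The only lower bound is consent: "If it falls before the ICF, then set the imputed start date to the ICF". A complete stop date can only pull the imputed start back to itself. First dose plays no part.
- **Wholly missing start, end date available.** Nothing is imputed. Instead "the position of the end date as either before or after the first dose date will be used to determine" TEAE status.
- **Both dates wholly missing.** "Completely missing start dates for AEs will be imputed as the start date of treatment, if the end date is completely missing".
- **Missing attributes.** "TEAEs will be considered treatment-related if relationship information is missing", and missing severity is treated as severe.

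Section 7.9.1 defines a TEAE as an event that starts or worsens from first dose until 30 days after last dose. It adds that "Imputed values for relationship, severity or onset date will be used for incidence summaries" and that "The AEs not considered to be a TEAE will be included in subject listings, but not summarized". Protocol section 9.4.4.1 has a similar TEAE window and no date-imputation rule, so nothing overrides section 6.3.

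**The concern.** Adverse events are collected from consent, and screening can last up to 12 weeks, so the TEAE split depends on where an onset falls relative to first dose. For a partial onset in the first-dose month, or a year-only onset in the first-dose year, the rule picks the earliest date it can. That date almost always precedes first dose.

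The incidence of AEs and SAEs is the trial's safety endpoint (SAP section 4.3). It is reported mainly through tables of TEAEs, treatment-emergent SAEs and treatment-emergent AESIs, and through exposure-adjusted rates. All of these inherit the misclassification. For day-missing dates the exposed window is the start of dosing, in what the protocol calls the first human study of the product.

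The rule also runs against the rest of its own section. Missing relationship, missing severity and wholly missing dates are all resolved toward counting the event. Only a partly known onset is resolved away from it.

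**Working it through.** The documents give no figure on this point, so there is none to reproduce. The check applies the rule literally and then counts how often it misplaces a true on-treatment onset. All dates below are assumed; the documents give no subject dates.

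**1. One subject.** Consent 20 January, first dose 10 March.

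| Recorded onset | Recorded stop | Onset used | TEAE? |
|---|---|---|---|
| March, day missing | 12 March | 1 March | No |
| March, day missing | missing | 1 March | No |
| Year only | 12 March | 1 January, raised to consent: 20 January | No |
| Wholly missing | 12 March | none; judged by the end date | Yes |
| Wholly missing | wholly missing | 10 March | Yes |

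The least informative records are counted and the more informative ones are not. Consent within the first-dose month does not help: with consent 3 September, first dose 15 September and onset recorded as September, the onset becomes 3 September.

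**2. Day missing, true onset in the first-dose month.** Take first-dose day d and onset day at or after d, all pairs equally likely. The imputed 1st precedes first dose whenever d > 1.

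- 30-day month: 30 × 31 / 2 = 465 pairs, of which 30 have d = 1. Misclassified: (465 − 30) / 465 = 435 / 465 = 93.5%.
- 31-day month: 31 × 32 / 2 = 496 pairs, of which 31 have d = 1. Misclassified: (496 − 31) / 496 = 465 / 496 = 93.8%.

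**3. Day missing, true onset in dosing days 1 to 14** (the two-week 5 mg step). An onset in the following month stays a TEAE, because the 1st of that month is after first dose.

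- 30-day month: 30 × 14 = 420 pairs. Onset is in the same month in 17 × 14 + (13 + 12 + … + 1) = 238 + 91 = 329. Removing the 14 with d = 1 leaves 315. 315 / 420 = 75.0%.
- 31-day month: 31 × 14 = 434 pairs. Same month in 18 × 14 + 91 = 343; 343 − 14 = 329. 329 / 434 = 75.8%.

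**4. Full calendar.** First dose on each day of a 365-day year, consent 7, 28, 56 or 84 days earlier, and every true onset from first dose to the end of that month (day missing) or that year (month and day missing).

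- Day missing: 21,492 of 22,952 misclassified = 93.6%.
- Month and day missing: 265,720 of 267,180 = 99.5%. The exceptions are first doses on 1 January.
- With first dose as the anchor: 0 and 0.

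Onsets recorded with a later month or a later year remain TEAEs. With only the day missing, the exposed window averages 15.7 of 280 treatment days (40 weeks), or 5.6%.

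**5. Weight of one subject.** SAP Table 1 plans 20 pediatric subjects per ADP101 dose and 10 + 10 = 20 on pooled placebo. One subject lost from a term is 1 / 20 = 5.0 percentage points. It is 1 / 40 = 2.5 points for pooled pediatric ADP101 and 1 / 24 = 4.2 points for all ages in one dose group.

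**The case against.** The percentages are conditional on a partial date in the exposed window, and largely restate that first dose seldom falls on the 1st. Partial dates there may be rare. First doses are observed in clinic for at least 2 hours. A telephone call follows each updosing visit, sites review a daily diary, visits are two-weekly, and SAEs and AESIs are reported within 24 hours. Year-only onsets are the least likely. This stands: the count is unknown and may be small.

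The 5-point figure applies only if the subject has no other TEAE under the same term, since subjects count once per term. An event-based rate loses one event. That stands as a condition on the figure.

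The event is not lost from the report. It stays in the listings and could appear under Screening in the by-period tables, which count each event in the period where it started (SAP sections 6.4.3 and 7.9.1). That is true, but Screening is the wrong period and the TEAE tables are not corrected.

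A first-dose anchor could also count some pre-dose events as TEAEs. Every randomized subject has had at least one Screening challenge reaction. If one were dated only to the first-dose month for both onset and stop, section 6.3 would put the stop at month end and the anchor would move the onset to first dose. Challenges are supervised, so this should be rare, and the error lies in the direction the section already accepts for relationship and severity.

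None of this supplies a first-dose check for partial start dates.

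**Conclusion.** The point holds. As written, a true on-treatment onset with a partial date in the first-dose month (or year, if the month is missing) is classed as pre-treatment. The exceptions are first dose on the 1st (1 January for a year-only date) and a recorded worsening after first dose.

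The shares in steps 2 and 3 of the check rest on uniform dates and apply only to day-missing records. The absolute effect on the tables cannot be computed, because the frequency of partial dates is not given. The error runs toward under-counting TEAEs. No bias between arms is claimed, and the efficacy analyses are untouched. The rule should still be changed: it bears on the safety endpoint in small groups, conflicts with its own section, and is easy to correct.

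**What to change.** Add to SAP section 6.3, under adverse-event dates: *If a partial AE start date is consistent with onset on or after first dose (same month and year, or same year if the month is missing) and the stop date is missing or not before first dose, impute the first-dose date.* Leave the 30-day TEAE window as it is.

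It is worth stating that a partial stop date is completed by the existing rule before this test. A stop in the first-dose month then resolves toward TEAE, and a stop in an earlier month keeps the event pre-treatment.

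The cost is one sentence and a programming change, with no new data. The trade-off is that a few true pre-dose events may be counted as TEAEs.

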7.6. Medications

Medications will be coded using the World Health Organization Drug Dictionary (WHODrug) B3 September 2020 version or later.

Subject incidence will be tabulated by Anatomic Therapeutic Class (ATC) level 2 and preferred term (PT), by treatment group and overall using the Safety Population. Subjects will be counted only once for each ATC level 2 or PT if they have multiple records of the same ATC or PT in the database. The incidences will be presented by ATC in descending order for the total column and then, within an ATC, by PT in descending order for the total column.

Medications detailed below will be summarized separately using the Safety Population.

All medications will be presented in by-subject data listings.

Prior and Concomitant Medications

Prior medication is defined as any medication received prior to the beginning of screening. Concomitant medication is defined as any medication continued or newly received at or after the beginning of screening. If a prior medication continues on or after screening, this prior medication will also be a concomitant medication.

Prior medications and concomitant medications will be summarized by treatment group.

Rescue Medications

For allergic reactions to food allergens that may occur during the DBPCFCs, subjects will be treated with epinephrine at the discretion of the investigator. Treatment of allergic reactions during the DBPCFCs, study drug dosing, and SPT may also require antihistamines, IV fluids, beta-adrenergic agonist (e.g., albuterol), oxygen, corticosteroids, and/or epinephrine, as indicated. Rescue medications will be identified by Yes responses to the Rescue Medication Question on the prior and concomitant medications source data.

These rescue medications will be summarized using the Safety Population. Rescue medications will also be summarized for Screening, Pre-Maintenance, Maintenance, Exit Food Challenge/Week 40 Visit, and Follow-Up Period.

Concomitant Procedures and/or Non-drug Therapies

Concomitant procedures and/or non-drug therapies will be coded using MedDRA version 23.0 or later. All concomitant procedures and/or non-drug therapies data will be presented in a by-subject listing using the Safety Population.

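### The consent-date floor in SAP 6.3 removes from the Prior table any partly dated medication that began before consent and continued past it

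*SAP*

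**What the plan says.** SAP 6.3, under Concomitant Medication Dates, completes a partial start to its earliest possible value: "Missing day will be imputed as the first day of month for all start dates", and "Missing month will be imputed as January for all start dates and as December for all stop dates". It then applies a floor at consent: "If it falls before the ICF date, then set the imputed start date to the ICF". The adverse-event paragraph of the same section has the same sequence in almost the same words.

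Two further checks follow. The first concerns complete stop dates: "If the stop date is complete, and the imputed start date is after the actual stop date, then the start date will be imputed" as that stop date. The second concerns imputed stops: "The imputed stop date will be compared to the last study date or death date" and capped there. An imputed stop is not compared with the start.

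SAP 7.6 sets the classification: "Prior medication is defined as any medication received prior to the beginning of screening". A drug continued or newly received from the beginning of screening is concomitant, and a prior drug that continues is also concomitant. SAP 6.2.3 makes the date of consent the first day of screening.

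For a completely missing start with a known end, 6.3 decides prior or concomitant by whether the end falls before or after the first dose, not the beginning of screening. No imputation is done for subjects who were never dosed.

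**The concern.** An adverse event is collected only from consent, so a consent floor does no harm there. A medication can begin years earlier, and the Prior table exists to show that. Protocol 6.8 lets subjects continue their usual asthma, rhinitis and atopic dermatitis drugs. A start known only to the month or year is plausible for such long-standing treatment. With the floor in place, a drug recorded as begun in 2018 and still taken is dated to consent. It no longer counts as received before screening, although 7.6 puts it in both tables.

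What is at stake is whether the Prior table follows the SAP's own definition, and whether the derived dates are coherent when both dates are partial.

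**Working it through.** There is no figure in the plan to reproduce. The check applies the 6.3 rules in their written order to example records and classifies the results by 7.6.

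Rules, all from SAP 6.3:

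1. A partial start goes to the first of the month, or to January if the month is missing. A partial stop goes to the end of the month, or of December.
2. An imputed start before consent is set to consent.
3. If the stop is complete and the imputed start is later, start = stop.
4. An imputed stop is capped at the last study or death date.

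Classification: prior if start < consent; concomitant if ongoing, or stop ≥ consent, or start ≥ consent.

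Assumed dates, for illustration only: consent 15 Sep 2021, first dose 20 Nov 2021, last study date 30 Oct 2022.

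| Recorded start | Recorded stop | Start after 6.3 | Stop after 6.3 | Class as written | Class with no floor |
|---|---|---|---|---|---|
| 2018 | ongoing | 15 Sep 2021 | none | concomitant only | both |
| Mar 2021 | ongoing | 15 Sep 2021 | none | concomitant only | both |
| Mar 2021 | 1 Dec 2021 | 15 Sep 2021 | 1 Dec 2021 | concomitant only | both |
| Mar 2021 | 10 Apr 2021 | 10 Apr 2021 | 10 Apr 2021 | prior only | prior only |
| Mar 2021 | Apr 2021 | 15 Sep 2021 | 30 Apr 2021 | start after stop | prior only |
| 2019 | 2019 | 15 Sep 2021 | 31 Dec 2019 | start after stop | prior only |
| 5 Mar 2021 | ongoing | 5 Mar 2021 | none | both | both |
| 5 Mar 2021 | Apr 2021 | 5 Mar 2021 | 30 Apr 2021 | prior only | prior only |

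- **Rows 1 to 3:** a drug that 7.6 places in both tables is lost from Prior.
- **Row 4:** rule 3 undoes the floor. The course stays prior with start = stop. Its true start is lost, but its class is right.
- **Rows 5 and 6:** rule 3 needs a complete stop, so it does not fire. In row 5 the start is 31 + 30 + 31 + 31 + 15 = 138 days after the stop (30 Apr to 15 Sep 2021). In row 6 it is 366 + 258 = 624 days after (31 Dec 2019 to 15 Sep 2021). Classified on the start, both would be concomitant. The SAP does not say how to class a record whose stop precedes its start.
- **Rows 7 and 8:** complete start dates are untouched.

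Cut date: take a drug with a completely missing start and a complete end between 15 Sep and 19 Nov 2021. By 6.3 it ended before the first dose, which points to prior. By 7.6 it was taken after screening began, so it is concomitant. Screening can last up to 12 weeks, so such end dates are possible.

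**The case against.** The strongest reply is that 7.6 defines status by when a drug was received, not by an imputed date. A drug recorded as started in 2019 could be classed from the year itself, and variable derivations sit in a separate programming document (SAP section 11). That is fair as far as it goes. But 6.3 ties date handling to deciding whether a medication is prior or concomitant, and nothing in 7.6 tells the programmer to ignore the imputed start.

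The second reply is that start-after-stop records should be rare. Protocol 6.8 asks for drugs being taken at screening or received during the study, so a course that ended before consent lies outside that instruction. Each such record would also need two partial dates. This stands, and it limits that part to a gap in the rules.

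The third is that the floor should not simply be deleted. Suppose only 2021 is recorded for a drug begun after the September consent. Without the floor it imputes to 1 January 2021, becomes prior, and starts before every period defined in SAP 6.4.3. This also stands and shapes the fix.

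A reader might infer that every partial start is moved to consent for good, or that all courses finished before consent become concomitant. Row 4 shows otherwise.

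A reader might also see an error in the rule that "Completely missing start dates for concomitant medications will be imputed as the start date of treatment, if the end date is completely missing". That is a convention for an unknown onset. Leaving the date blank, or calling every such drug both prior and concomitant, is a preference.

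**Conclusion.** The concern holds in a limited form. For dosed subjects, a drug with a partial start known to precede consent, and taken beyond consent, is re-dated to consent and drops out of the Prior table, contrary to 7.6. It remains correctly in the concomitant table. When the stop is also partial and imputes to before consent, the record ends up with its start after its stop and its class undefined. The two cut dates are a separate inconsistency.

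This assumes that status is derived from the imputed start. Every record of the described type is affected, but the number cannot be estimated because the documents do not report how often dates are partial. A claim that the Prior table would be nearly empty is therefore unsupported.

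Wider harm is tempting to infer, but the planned outputs do not support it:

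- The tables in 7.6 are subject incidence by drug class and preferred term, with no category for newly started drugs.
- Only rescue medications are summarised by period there, and they are identified by a Yes response.
- Prior medications are not among the baseline characteristics listed in 7.3.
- Nonpermitted drugs reach the Per Protocol Population through protocol-deviation review (5.4 and 7.2).

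The effect stops at descriptive medication tables, and at listings if they show derived dates or status. No efficacy endpoint, test or adverse-event status changes.

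**What to change.** In the medication part of SAP 6.3:

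1. Apply the consent floor only when the known part of the start date is compatible with a start on or after consent, that is, the same month, or the same year with the month missing. If the known month or year is before consent, keep the imputed pre-consent date. The medical and allergy history rule in 6.3 already conditions on whether the known parts match the consent date, so there is a model in the same section.
2. Require imputed start ≤ imputed stop when the stop is partial as well, for example by extending the complete-stop rule to imputed stops. This is still needed after step 1. In the example, a start of 2021 with a stop of April 2021 would be floored to 15 Sep 2021, after its imputed stop of 30 Apr 2021.
3. Use one prior/concomitant cut date in 6.3 and 7.6.

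Leave the floor in place for adverse events. With steps 1 and 2, all eight example records take the class in the last column of the table and none has its start after its stop.

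The cost is a few lines of SAP text and a change to one derivation. No new data are needed and nothing changes for subjects.
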